# 13.2.4. Safety Endpoints

- The incidence, severity and frequency of all Adverse Events (AE), related and unrelated to the device treatment including seizures.
- Cognitive changes using the Mini Mental State Exam (MMSE) and the Buschke Selective Reminding Test (BSRT) cognitive tests.
- Vital signs and hearing loss measured by auditory threshold testing will be evaluated.

### 13.3. Study Hypothesis

In this study we will test the following hypotheses:

- $H_0: CQR_{DTMS} = CQR_{SHAM}$
- $\bullet \quad H_1: \ CQR_{DTMS \neq} \ CQR_{SHAM}$

Where:  $CQR_{DTMS}$  is the continuous quit rate in the DTMS arm and  $CQR_{SHAM}$  is the continuous quit rate in the Sham group.

### 13.4. Sample size

The preliminary clinical study evaluated the safety and efficacy of the DTMS as an aid in smoking cessation, at three weeks and at six months follow-up. The three week point prevalence quit rate was 44% in the treatment group and 13% in the sham group. The six month point prevalence quit rate was 33% in the treatment group and 9% in the sham group. Although, the three week point prevalence quit rate showed a significant improvement in the treatment group compared to the sham group, the point prevalence quit rate did not meet the standard requirement for evaluating smoking cessation, i.e., at least a 4 week continuous quit rate. Furthermore, the six month data had its limitations, including a long term time point and high drop-out rate. Therefore, we looked at the clinical results provided in support of FDA approval of other smoking cessation aids, including Zyban (Bupropion hydrochloride) and Chantix (Varenicline). The mechanism of action of Zyban which aids smoking cessation is the increase in dopamine release, which is also one of the mechanisms of action of the DTMS treatment.

The quit rates (i.e., based on abstinence from week 4 of the study through week 7) were 49% in the treatment group receiving Zyban compared to 36% in patients receiving Nicotine Replacement Therapy (NRT) and 23% in the placebo group. In two other studies, subjects treated with Chantix had an abstinence rate during weeks 9 through 12 of 44% compared to 30% in patients treated with Zyban and 17% and 18% in patients receiving placebo.

For the purpose of sample size calculation the weighted average of the quit rates for smoking cessation treatments (including Zyban, Chantix, NRT and DTMS) (38.6%) and the weighted average of the quit rates for placebo/sham (18.4%) will be used. Using the above weighted averages we can assume a placebo/sham success rate of 18%, and a minimally important difference of 20%.

The study is designed to have 80% power with a two-sided level of significance of 5% to detect to detect a difference of 20% in the CQR in the DTMS group compared to the control group, and one planned interim analyses using the Lan De-Mets alpha spending approach with a Pocock type spending function (the calculations were performed using the SAS SEQDESIGN procedure).

Given this design we will require a total number of 164 (82 per arm) subjects at most. Allowing for a potential 37% drop-out 270 subjects will be randomized. The dropout rate was continuously monitored in a blinded way, and the total number of subjects to be enrolled was adapted accordingly.

### 13.5. Interim Analysis (was not performed – will be detailed in the SAP)

One (1) interim analysis is planned after 106 subjects (approximately 65% information) will complete at least the 6 week visit. The main goal of this interim analysis is to stop the study in case of success, i.e. the CQR in the DTMS group is statistically significantly higher than that in the sham arm.

### 13.4.1. Procedure

After all the relevant data will be entered into the database and a soft lock to the database will be performed. An independent un-blinded statistician (not the study statistician) will perform the assessment of the primary and safety endpoints. In order to maintain scientific integrity of the study, no major protocol changes will be made after the interim analysis.

# 13.4.2. Blinding

ONLY the un-blinded statistician and members of the interim decision committee will be exposed to the interim report. All parties having access to the interim analysis will be identified and documented. The members of the DSMB may also have access to the unmasked information of the interim analysis if requested by the DSMB chairman. Investigators and company directors will only be informed of a decision to continue or to discontinue the trial, or to implement modifications in trial procedure. The un-blinded statistician who is responsible for conducting the interim analyses should ensure that the unmasked data is not available to any unauthorized person within or outside the company.

### 13.4.3. Decision Rules

The following decisions upon the interim analysis report are planned:

- Stop the study in case of severe safety concerns.
- Stop the study in case of success i.e. if the CQR in the DTMS group is statistically significantly higher (p<0.03154) than in the sham arm.
- Otherwise, continue the study without changes in the protocol.

### 13.4.4. Alpha level

The study is designed as a group sequential study with one planned interim analysis with a Pocock type spending function using the Lan De-Mets alpha spending approach. The study hypothesis will be tested at the time of the interim analysis. If the 2-sided p-value of the comparison of the primary endpoint (CQR) between the two study arms is statistically significant, i.e. <0.03154, the study will be stopped and considered successful. Otherwise, the primary endpoint will be tested at the end of the planned study for a level of significance of 3.154%.

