# **13. STATISTICAL CONSIDERATIONS**

### 13.1. Study Design and Objectives

This is a prospective, randomized, 4 month, double blind, controlled trial in outpatients recruited from hospitals and clinics, using a sequential two-stage adaptive design with one interim analysis at approximately 65% of the expected information.

The aim of this study is to evaluate the safety and efficacy of DTMS compared to sham treatment as an aid to smoking cessation in chronic (>10 cigarettes/day) cigarette smokers.

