### 13.6. Randomization

A subject meeting the eligibility criteria will be equally allocated (with a 1:1 ratio) to one of the following 2 treatment groups based on a randomization scheme with blocks stratified by center:

- 1. DTMS
- 2. Sham

The randomization scheme will be prepared by the study statistician using the SAS® (version 9.3.) random number procedure. The block size will be variable and study personnel will be blinded to the randomization block size.

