### 13.9.2. Significance levels and handling of type I error

The overall significance level for this study is 5% using two-tailed tests, except for the treatment by site interaction that will be tested at a significance level of 10%.

The hierarchy approach will be adopted for the primary and secondary endpoints to control the type I error due to multiple endpoint testing. Thus, the primary endpoint will first be analyzed and only if found statistically significant as detailed in section 13.4, will the first secondary endpoint be analyzed; and only if found statistically significant, will the second secondary endpoint be analyzed. This approach will maintain the overall study type I error by continuing to analyze the next end-point in the hierarchy only if the previous endpoint analysis was found significant.

The exploratory end-points will not be part of the hierarchy as descriptive statistics are mainly planned.

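### Section 13.5 says the interim analysis was not performed, but the only level printed for the final primary test is still the two-look 3.154%; the error is conservative but costs power, and the boundary is misnamed.

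*Protocol*

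**What the plan says.** - Section 13.1 describes the trial as "using a sequential two-stage adaptive design with one interim analysis at approximately 65% of the expected information".
- Section 13.4 (Sample size) states: "The study is designed to have 80% power with a two-sided level of significance of 5" per cent. It plans for "one planned interim analyses using the Lan De-Mets alpha spending approach with a Pocock type spending function". It requires at most 164 subjects (82 per arm) and randomizes 270 to allow for 37% drop-out.
- Section 13.5 is headed "Interim Analysis (was not performed – will be detailed in the SAP". The text beneath still describes one look after 106 subjects, about 65% information.
- Sections 13.4.3 and 13.4.4 (so numbered, although they follow 13.5) stop for success at p < 0.03154. Section 13.4.4 then says: "Otherwise, the primary endpoint will be tested at the end of the planned study for a level of significance of 3.154" per cent.
- Section 13.9.2 says: "The overall significance level for this study is 5% using two-tailed tests". It tests the first secondary endpoint only if the primary is significant as detailed in Section 13.4, and the second only if the first succeeds.

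**The concern.** A two-look boundary lowers the final level to pay for the chance of an early false positive. If the early look is not taken, there is nothing to pay for. Under the alpha-spending approach that the protocol names, an analysis that does not happen spends nothing, and the single final analysis carries the full two-sided 5%. The document records that the look did not happen but keeps the reduced level, so 13.4.4 no longer fits 13.5 or the 5% in 13.4 and 13.9.2.

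What is at stake is the success criterion. A primary p-value between 0.0315 and 0.05 would meet the stated overall level and fail the printed final level, and it would decide whether either secondary endpoint is tested. A single test at 3.154% also has less power than the two-look design for which 82 per arm was calculated.

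The figure and the named method disagree as well: someone applying the Lan-DeMets Pocock-type function at 65% information would not obtain 0.03154 at either look.

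**Working it through.** **Inputs.** Two-sided overall alpha 0.05 (13.9.2). Power 80%, sham 18%, difference 20 points, hence 38% on DTMS (13.4: "we can assume a placebo/sham success rate of 18%, and a minimally important difference of 20" per cent). Allocation 1:1 (13.6). Interim at 106 of 164, i.e. 106/164 = 0.646, stated as about 0.65 (13.5). Level 0.03154 at both looks (13.4.4). 82 per arm required, 135 per arm randomized, 37% loss (13.4).

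**Step 1: reproduce 0.03154.** Take the two test statistics as bivariate normal with correlation √0.65. The constant critical value that gives overall two-sided alpha of 0.05 is z = 2.1503, nominal p = 0.03153. At t = 0.646 it is 0.03147. Using 0.03154 at both looks with t = 0.65 gives overall alpha of 0.0500. The printed figure is therefore the classical constant Pocock boundary.

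**Step 2: reproduce 164.** With that boundary, 80% power needs a drift of 2.914. The unpooled variance sum is 0.38×0.62 + 0.18×0.82 = 0.3832. Then n = 2.914² × 0.3832 / 0.20² ≈ 81.4 per arm, rounded up to 82, or 164 in total. Two-look power at 82 per arm is 80.3%. The sample size belongs to the same boundary.

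**Step 3: the named function.** Lan-DeMets Pocock-type spending is α(t) = 0.05 × ln(1 + (e − 1)t). At t = 0.65 this is 0.05 × ln(2.117) = 0.0375. Solving for the final level gives 0.0249. At t = 0.646 the pair is 0.0373 and 0.0250. The function gives 0.03154 at the interim only for t near 0.51, and at the final analysis only for t near 0.36, so no single timing gives it at both looks. It would also need about 169 subjects rather than 164 (unpooled).

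**Step 4: power with one final look.** Unpooled power = Φ(0.20 / √(0.3832/n) − z), with z = 2.150 for 3.154% and 1.960 for 5%.

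At n = 82: 0.20 / √(0.3832/82) = 2.926.
- At 3.154%: Φ(2.926 − 2.150) = Φ(0.776) = 78.1%.
- At 5%: Φ(2.926 − 1.960) = Φ(0.966) = 83.3%.

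The pooled version puts √(2×0.28×0.72/n) in the critical value.

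| Evaluable per arm | Variance | Final test at 3.154% | Final test at 5% |
|---|---|---|---|
| 82 (required) | unpooled | 78.1% | 83.3% |
| 82 | pooled | 76.4% | 82.0% |
| 85 (135 × 0.63) | unpooled | 79.6% | 84.6% |
| 85 | pooled | 78.0% | 83.4% |
| 135 (no loss) | unpooled | 94.6% | 96.4% |
| 135 | pooled | 93.9% | 95.9% |

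**Step 5: alpha left unused.** 5% − 3.154% = 1.846 percentage points.

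**The case against.** The best defence is textual. The 3.154% sentence opens with a conditional: it is the branch that follows an interim test that was run and not passed. No sentence says that 3.154% applies when no look is taken, and the heading of 13.5 leaves the detail to the SAP, which may restore 5%. The reference in 13.9.2 to Section 13.4 also reaches the 5% in the sample-size text. All of this stands. A reader might infer that the trial is certain to be tested at 3.154%, and the protocol does not establish that. What it does show is that 3.154% is the only numeric level printed specifically for the final primary test, and that nothing replaces it now that the look has been dropped. An SAP at 5% would then differ from the protocol on the success criterion.

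A reader might also infer that error control is broken or that 0.03154 is an invalid boundary. Neither follows. Testing once at 3.154% is conservative and does not bias the estimate. Used at both looks, 0.03154 holds overall alpha at 0.0500. Once no look is taken, the wrong label changes no decision.

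Nor do the figures support calling the trial underpowered in general. The shortfall is clear at 82 per arm and slight at 85. The efficacy set needs only one post-baseline assessment (13.8.1) and dropouts count as non-abstinent (13.9.8), so more than 82 per arm may be analysed. Against that, counting dropouts as failures may shrink the difference below 20 points.

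**Conclusion.** The point holds as an unreconciled passage with a real but limited cost. If the final test is run once at the printed level, the type I error is 3.154% against the stated 5%, and power at the planned 82 per arm is 76% to 78% instead of at least 80%. The loss against a 5% test is 5 to 6 points at 82 per arm, about 5 points at 85, and about 2 points if all 135 per arm are evaluable. These figures assume 18% versus 38%, a normal approximation and no unblinded efficacy look. The wrong boundary name is a separate and smaller fault.

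This should be fixed because it settles the primary success criterion and the route to both secondary endpoints. It is not a threat to the validity of the trial.

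**What to change.** Before unblinding:

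1. In 13.4.4, state that no interim look was taken, that no alpha was spent, and that the final primary test is at two-sided 5%.
2. Document that the interim was dropped without sight of unblinded efficacy data. The statement should cover the DSMB, which reviews accumulated data every six months (17.5) and may see unmasked interim results on request (13.4.2).
3. Mark 13.4.1 to 13.4.3 as not applicable rather than deleting them, so that the pre-specified plan stays on record.
4. Align 13.1, 13.4 and the SAP with a single final analysis, and make the cross-reference in 13.9.2 point to the revised level.
5. Correct the boundary's name: 0.03154 is the constant Pocock boundary at 65% information, not Lan-DeMets Pocock-type spending.

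If any unblinded efficacy look did occur, keep the adopted two-look boundary, or derive the remaining alpha from the function actually adopted.

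The cost is wording only, with no added subjects or data, provided the data are still blinded. The protocol does not show that they are: its past-tense remarks on drop-out monitoring indicate a revision made during the study. The blinding record is therefore what makes a move to 5% credible.

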### 13.6. Randomization

A subject meeting the eligibility criteria will be equally allocated (with a 1:1 ratio) to one of the following 2 treatment groups based on a randomization scheme with blocks stratified by center:

- 1. DTMS
- 2. Sham

The randomization scheme will be prepared by the study statistician using the SAS® (version 9.3.) random number procedure. The block size will be variable and study personnel will be blinded to the randomization block size.

#### 13.7. Blinding

The subjects, investigators, raters, and device operators will all be blinded regarding the treatment received. The treatment allocation will be coded into a subject personal card that will be inserted into the device. The device will produce DTMS or Sham treatment according to the pre-programmed card.

### 13.8. Data Analysis Sets

13.8.1. Intent-to-Treat (ITT) Analysis Set

For safety analysis, the ITT analysis set (ITT-S) will consist of all subjects randomized. In accordance with the ITT principle, all subjects randomized who received at least one treatment (DTMS or Sham) will be kept in their originally assigned treatment group. For efficacy analyses, the ITT analysis set (ITT-E) will consist of all subjects who met all the inclusion/exclusion criteria and were randomized who received at least one treatment (DTMS or Sham) (defined as an average stimulation intensity of at least 110% of the motor threshold during treatment session no. 3 to the last treatment session) and have at least one post-baseline assessment available for analysis.

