## 3.4.Principles of Use

The HADD-Coil device technology is based on applying deep brain TMS by means of repetitive pulse trains at a determined frequency. A pre-selected treatment protocol is assumed to activate deep brain regions and their interconnecting fibers. This, in turn, may affect the mechanisms involved in the pathophysiology of mental illnesses on one hand, as well as the rewarding circuits, motivation and pleasure on the other hand.

The treatment protocol will start with localization of the optimal spot on the scalp for stimulation of the right abductor pollicis brevis muscle and determination of the individual motor threshold. The coil will then be placed 6 cm anterior to the motor spot.

Each daily treatment session will consist 60 rTMS trains of 10 Hz for 3 seconds with inter-train interval (ITI) of 15 seconds (a total of 1800 stimuli per session) over the prefrontal and insular cortices. Subjects in the control group will receive sham treatment in a similar manner. In the inactive sham treatment, some of the HADD-Coil windings are disconnected and no electric current flows through them. Additionally, the HADD-Coil windings are connected in series to a secondary coil, which is located at the connection between the cooling air pipe and the helmet, far from the patient head. The role of the secondary coil is to increase the auditory output and increase the overall coil inductance. Increasing the inductance leads to a decrease in the output electric field of the coil in the sham mode.

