11.3.1. Abstinence and Continuous Quit Rates (CQR)

Abstinence is defined as a subject's self-report (section 11.3.1) of no smoking (0

cigarettes/day), confirmed by urine cotinine levels  $\leq$ 200ng/ml (section 11.3.2). The "cutoff" value of urine cotinine) is recognized as 200 ppm or 200ng/ml) for the determination of abstinence. Subjects with cotinine levels above this value will be considered to have not stopped smoking. Continuous Quit Rates (CQR) is defined as the ratio of the number of patients meeting the quit criterion (i.e., abstinence during a consecutive 4 week period) to the number of patients initially treated, will be assessed at Baseline, at the weekly visits during the treatment phase and at the 4 month follow-up visit.

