### 13.2. Study Endpoints

# 13.2.1. Primary Efficacy Endpoint

The primary endpoint is the four-week continuous quit rate (CQR), representing abstinence during a consecutive 4 week period. Weekly abstinence is defined as a subject's self-report (in diary) of no smoking (0 cigarettes/day during the whole week), confirmed by urine cotinine levels  $\leq 200$  ng/ml. A missing confirmatory test will be considered negative, if the previous and the following weekly or 4 month follow-up confirmatory tests are negative. Quit rates are defined as the ratio of the number of patients meeting the quit criterion for at least 4 consecutive weeks to the number of patients initially treated and having at least one post-baseline assessment.

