# 13.9.8. Handling of missing data

If a subject missed a clinic visit but had been abstinent (i.e., a negative confirmatory test) at the clinical visits prior to and following the missing visit, and claimed abstinence throughout, that subject will be classified as abstinent. Dropouts and subjects lost to follow will be classified as non-abstinent.

Additionally, the following methods of imputation may be used for the primary endpoint as further sensitivity analyses:

- Tolerability/Imputation: Assume all subjects terminated from the study due to tolerability issues are failures. For other subjects, the outcome will be obtained from the last valid assessment.
- Last Observation Carried Forward: Most recent visit with a valid assessment will be carried forward and used for the endpoint determination for these subjects.
- Multiple Imputation: Impute endpoint data using a multiple imputation model based on sex, age, race and history of smoking at baseline, as well as endpoint data computed at each intermediate time-point for all subjects with observed data.
- Best Case Scenario: Assume all subjects with missing data in the active group are successes; Assume all subjects in the sham group with missing data are failures.
- Worst Case Scenario: Assume all subjects with missing data in the active group are failures; Assume all subjects in the sham group with missing data are successes.

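### The primary efficacy set labelled ITT-E removes randomised, treated subjects on a condition known only after randomisation, so the primary test can lose its stated error rate in either direction

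*Protocol*

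**What the plan says.** Section 13.8.1 (Intent-to-Treat Analysis Set) sets three conditions for a randomised subject to enter ITT-E. The subject must have met all eligibility criteria, must have at least one post-baseline assessment, and must have received at least one treatment. That treatment is then qualified as "defined as an average stimulation intensity of at least 110% of the motor threshold during treatment session no. 3 to the last treatment session". Section 13.8.3 makes ITT-E the main efficacy set and names the completer (CO) and per-protocol (PP) sets as sensitivity sets. Both are defined as subsets of ITT-E. The set of all randomised subjects, ITT-S, serves safety only.

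The denominator of the primary continuous quit rate (CQR) is given in three forms:

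- Section 11.3.1 uses "the number of patients initially treated, will be assessed at Baseline" and the later visits, with no further condition.
- Sections 1, 5.1 and 13.2.1 use the "number of patients initially treated and having at least one post-baseline assessment".
- Section 13.8.1 adds the intensity and eligibility conditions.

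Section 13.9.8 states: "Dropouts and subjects lost to follow will be classified as non-abstinent".

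**The concern.** The intensity condition can be evaluated only from what happens in sessions 3 onward. Within one sentence, a subject who had one or two sessions satisfies the one-treatment requirement and fails its definition. Such a subject has left treatment early, and Section 13.9.8 would count a drop-out as a failure. That rule cannot act on someone already outside the set.

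The post-baseline requirement may remove early leavers too. Weekly assessment visits start at week 2 (Section 11.1.4), but craving is rated at each treatment (Section 11.2.3) and diaries are kept daily (Section 11.2.1). Whether a subject who leaves in week 1 stays in depends on whether those records count as an assessment, which the protocol does not say.

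At stake is the basis of the primary p-value. Once membership depends on events after randomisation, the groups compared are no longer the randomised ones. Any difference in who is removed enters the estimate.

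**Working it through.** **The plan's own figure first.** Section 13.4 assumes 18% in sham and a 20-point difference (so 38% in active), 80% power, two-sided 5% and one interim look. Section 13.5 puts that look at about 65% information. A constant Pocock boundary at that point gives a critical value of 2.150, a nominal p of 0.0315 (Section 13.4.4 states 0.03154) and a required drift of 2.914. Then

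n per arm = 2.914² × (0.38×0.62 + 0.18×0.82) / 0.20² = 81.4, so 82 per arm and 164 in total, as stated.

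The inputs are therefore read correctly. The plan randomises 270, or 135 per arm (Section 1).

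**Effect of exclusion under no true effect.** Inputs from the protocol: a true CQR of 18% in both arms (the planning sham rate), 135 per arm and a chi-squared test (Section 13.9.5). Assumed: the shares excluded, e_A (active) and e_S (sham), and the quit rate r among the excluded. The rate seen in an arm is

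(0.18 − e × r) / (1 − e).

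For e_A = 20%, e_S = 5% and r = 0:

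- Active: 0.18/0.80 = 22.5% of 135 × 0.80 = 108.
- Sham: 0.18/0.95 = 18.9% of 135 × 0.95 = 128.25.
- Pooled rate: (24.3 + 24.3)/236.25 = 20.6%.
- Standard error: √[0.2057 × 0.7943 × (1/108 + 1/128.25)] = 0.0528.
- Shift in the test statistic: (0.2250 − 0.1895)/0.0528 = 0.67.
- Chance of significance favouring active: P(Z > 1.96 − 0.67), about 9.9%.

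Simulation of the test itself (1,000,000 trials per scenario) gives 10.1%. Both the 5% level and the 3.154% level of Section 13.4.4 are shown, because the heading of Section 13.5 says the interim was not performed and the final level is then unclear.

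| Excluded active / sham | Quit rate of excluded | Rates seen, active / sham | False positives favouring active, 5% level (nominal 2.5%) | Same, 3.154% level (nominal 1.6%) |
|---|---|---|---|---|
| 10% / 5% | 0% | 20.0% / 18.9% | 4.1% | 2.6% |
| 15% / 5% | 0% | 21.2% / 18.9% | 6.4% | 4.4% |
| 20% / 5% | 0% | 22.5% / 18.9% | 10.1% | 7.1% |
| 25% / 5% | 0% | 24.0% / 18.9% | 15.4% | 11.4% |
| 20% / 5% | 9% | 20.2% / 18.5% | 5.5% | 3.6% |
| 20% / 5% | 18% | 18.0% / 18.0% | 2.6% | 1.6% |
| 10% / 10% | 0% | 20.0% / 20.0% | 2.5% | 1.6% |
| 5% / 20% | 0% | 18.9% / 22.5% | 0.4% | 0.2% |

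In the last row the error moves to the other side: the two-sided error is 10.5% at the 5% level and 7.4% at the 3.154% level.

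**With all randomised subjects kept** and the excluded counted as non-abstinent, both arms stay at 18%. The two-sided error is 5.1% at the 5% level and 3.2% at the 3.154% level, which is nominal apart from the approximation in the test.

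**The case against.** The strongest reply is that the protocol does not show the conditions for bias. Several stronger readings are tempting, and the text does not carry them.

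- *Active loses more subjects, so the bias favours the device.* Section 3.4 says of the sham that "Increasing the inductance leads to a decrease in the output electric field of the coil in the sham mode", which makes a difference in tolerability plausible. But Section 3.1 says the sham is built to imitate the sound, the scalp sensation and the facial muscle activation. Section 9 gives it identical parameters, and Section 2.4 reports good tolerability apart from transient headaches. Direction is not established.
- *The removed subjects are nearly all non-quitters.* This is fair for early drop-outs under the plan's own rule. It does not follow for someone who averages below 110%, completes six weeks and is assessed.
- *Anyone who cannot reach full intensity is removed.* The regular intensity in Section 9 is 120%. A subject held at 110% throughout stays in.
- *Eligibility is reviewed after randomisation.* No such review is described. Eligibility is a status before randomisation, so this condition is the weakest part.
- *The 37% in Section 13.4 indicates how many are excluded.* It is a total drop-out allowance. Drop-outs who meet the ITT-E conditions stay in and count as failures.

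It can also be said that Section 13.9.8 offers worst-case and tolerability imputations. These are optional, and they address missing outcomes. Under Section 13.8.3 the primary efficacy assessment runs on ITT-E, CO and PP, so nothing states that they bring back excluded subjects. The denominator discrepancy is partly one of wording, since Sections 1, 5.1 and 13.2.1 agree with each other.

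These points limit the claim about size and direction. They do not touch the definition itself.

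**Conclusion.** The point holds as a defect in a stated rule. The set called ITT-E is conditioned on treatment received after randomisation, contradicts itself on what one treatment means, and is primary. No efficacy set undoes it.

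The consequence is conditional. Error inflation needs exclusion to differ by arm and excluded subjects to quit at a different rate from the rest. Under the assumption that all excluded subjects are non-quitters, the false-positive rate favouring active runs from 4.1% to 15.4% (nominal 2.5%) as active exclusion goes from 10% to 25% against 5% in sham. It is near nominal if exclusion is equal or if excluded subjects quit at the common rate, and the bias reverses if sham loses more. A reader might infer that the primary result is bound to favour the device. The protocol gives no exclusion rates by arm, so it supports only that the test can be biased, in either direction. The contradiction in Section 13.8.1 needs correcting whatever those rates turn out to be.

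**What to change.** Change the analysis sets only; nothing here concerns how subjects are treated.

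1. Define the primary efficacy set as all randomised subjects, analysed as allocated. At the least, include everyone who received any session at any intensity; that version still omits randomised but untreated subjects and should be labelled as modified.
2. Count drop-outs and subjects without post-baseline data as non-abstinent, as Section 13.9.8 already does for drop-outs.
3. Move the 110% average-intensity condition, and the eligibility condition if wished, to the PP set or a supportive set.
4. Use this one denominator in Sections 1, 5.1, 11.3.1, 13.2.1 and 13.8.1.

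The cost is wording plus some power, because quit rates fall in both arms. With 135 per arm, if a share f of each arm counts as non-abstinent and the rest quit at 38% and 18%, the rates become 0.38(1 − f) and 0.18(1 − f):

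| f | Rates | Power at 5% | Power at 3.154% |
|---|---|---|---|
| 10% | 34.2% / 16.2% | 93% | 90% |
| 20% | 30.4% / 14.4% | 89% | 85% |
| 37% | 23.9% / 11.3% | 78% | 72% |

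Only if the full 37% allowance counts as failures does power fall below the planned 80%.
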